	
 • Skin feature score of at least 2 OR • Joints and fascia score of at least 1 
4. New, stable or progressive sclerosis/fasciitis despite treatment with at least one prior line of systemic therapy for cGVHD.
 
5. Female patients who:
 
 • Are documented to be postmenopausal or are surgically sterile, OR • If of childbearing potential, agree to use at least 1 highly effective method of contraception from the time of signing the informed consent form through 30 days after the last dose of study drug, OR agree to practice true abstinence or exclusively non-heterosexual activity when this is in line with the preferred and usual lifestyle of the subject 
6. Male patients who:
 
 • Are surgically sterile (vasectomized) OR • Agree to use at least 1 highly effective method of contraception during the entire study treatment period and through 30 days after the last dose of study drug, OR agree to practice true abstinence or exclusively non-heterosexual activity when this is in line with the preferred and usual lifestyle of the subject, AND • Agree to use a condom to prevent potential transmission of investigational drug in seminal fluid 
7. Patients who meet the following clinical laboratory criteria:
 
 • Absolute neutrophil count (ANC) > 1000/μL, platelet count > 50×10^9/mL • ALT and AST < 2x ULN and normal total bilirubin unless attributed to cGVHD • Creatinine < 2.0 mg/dL
--	---

Exclusion Criteria:	
 1. Hospitalization for evaluation or management of an infection within the last 8 weeks 2. Known organ dysfunction 
 • uncontrolled cardiovascular disease, including arrhythmias, congestive heart failure • oxygen requirement 3. Addition of any new systemic immunosuppressive treatment within the last 2 weeks. 
 • Addition of new systemic immunosuppressive treatment along with glasdegib is also prohibited 4. QTc interval > 480 ms 5. Female patients who are lactating or have a positive serum pregnancy test 6. Major surgery within 14 days before enrollment 
 • Does not include placement of venous access device, bone marrow biopsy, GVHD diagnostic biopsy, or other routine procedures in cGVHD or post-transplantation care 7. Use of any concomitant medications that are prohibited within the past 7 days 8. Any serious medical or psychiatric illness that could, in the investigator's opinion, potentially interfere with the completion of treatment according to this protocol 9. Known intolerance to glasdegib, sonidegib, or vismodegib 10. Non-hematologic malignancy within the past 2 years with the exception of: 
 • adequately treated basal cell carcinoma, squamous cell skin cancer, or thyroid cancer • carcinoma in situ of the cervix or breast
----------------------------	--

	
 • prostate cancer of Gleason Grade 6 or less with stable prostate-specific antigen levels • cancer considered cured by surgical resection or unlikely to impact survival during the duration of the study 
11. Treatment with non-FDA approved drug within 28 days of start of this trial
 
12. Evidence of recurrent or progressive underlying malignant disease
 
13. Karnofsky performance status (KPS) < 70%
 
14. History of non-compliance
 
15. Life expectancy < 6 months
 
16. Grade 2 or 3 muscle cramping, or grade 1 muscle cramping that occurs at least weekly.

Concomitant Medications:	
Permitted Concomitant Therapy
 
 • Ongoing systemic treatment for acute GVHD prophylaxis, acute GVHD treatment, or cGVHD treatment • Prophylaxis against infection 
Prohibited Concomitant Therapy
 
 • moderate/strong CYP3A4 inducers 
Avoid Unless No Other Alternative
 
 • moderate/strong CYP3A4 inhibitors • drugs with known risk of Torsades de Pointes • QT prolonging medications

1.0 BACKGROUND INFORMATION

1.1 CHRONIC GRAFT-VERSUS-HOST DISEASE

Chronic graft vs. host disease (cGVHD) is a major late complication of allogeneic hematopoietic cell transplantation (HCT) that affects up to 50% of HCT survivors. The syndrome is associated with major transplant-related morbidity, mortality, infectious complications, prolonged duration of immune suppression, and impaired patient-reported quality of life.¹⁻⁸ Thus, it represents a major obstacle to recovery and survival following HCT, and its prevention and treatment are of significant importance. Chronic GVHD is characterized by diverse clinical manifestations, but the most commonly affected organs are the skin, eyes, mouth, and liver.⁹ However, most organs can be involved, with parallels to other systemic immune-mediated disorders.

Sclerotic GVHD is a distinctive phenotype of cGVHD that usually begins in the superficial layers of the skin and then extends to deeper layers but it may also only involve deeper structures such as fascia with normal overlying skin. Sclerotic GVHD can severely affect patients' mobility and quality of life, and it is often refractory to standard and secondary therapies. The presence of sclerosis after allogeneic HCT is considered diagnostic for cGVHD.¹⁰ Progressive or poorly controlled sclerotic GVHD results in joint contractures, chronic skin ulcers, and pulmonary restriction, causing major disability. A prospective multicenter observational study found a cumulative incidence of 8% sclerosis with a median onset of 14 months.¹¹ In a large study from Fred Hutchinson Cancer Research Center, the cumulative incidence of sclerosis was 20% at 3 years. Of the patients who developed sclerosis, 13% had only skin sclerosis, 33% had only joint contracture or fasciitis, and 53% had both clinical manifestations. The development of sclerosis was associated with a reduced rate of withdrawal of immunosuppressive treatment.¹² These findings as well as clinical experience indicate that patients with sclerotic chronic GVHD have poor quality of life, often require multiple sequential therapies, and frequently exhaust available treatment options.¹³⁻¹⁵

1.2 CHRONIC GVHD DIAGNOSIS AND CLASSIFICATION

Diagnosis and classification of cGVHD has undergone major revision following the 2005 and 2014 NIH Consensus Conferences on Chronic GVHD. The diagnosis of cGVHD is based on the presence of diagnostic manifestations of the syndrome or distinctive manifestations supported by confirmatory biopsy or testing. Chronic GVHD severity is scored according to objective criteria for each organ involved, which is summarized by an overall global severity score of mild, moderate, or severe (Appendix 1).^{10,16} Mild disease is generally well-tolerated and may sometimes be managed with topical or local therapies. Moderate and severe disease is

associated with higher mortality and requires systemic treatments.¹⁷ Patients with moderate-severe disease and sclerosis will be enrolled in this trial.

1.3 THERAPY OF ESTABLISHED CHRONIC GVHD

Accepted standard primary therapy for cGVHD includes 0.5-1 mg/kg of prednisone or equivalent with or without a calcineurin inhibitor.^{1,18,19} The addition of other systemic immune-suppressive agents to initial therapy has not provided benefit, as evidenced by trials adding azathioprine, thalidomide, hydroxychloroquine, mycophenolate mofetil and entospletinib to initial treatment with steroids.²⁰⁻²³ Published primary cGVHD therapy trials demonstrate that on average 27% will achieve complete response, and 60% will achieve overall response (complete + partial response) by 6-9 months after starting initial therapy.^{18,20-24} A study testing the addition of ibrutinib to standard primary therapy has almost finished accrual as of December 2018.

Based on insufficient response to primary therapy or a flare of cGVHD after tapering of initial therapy, many will go on to require additional immune-suppressive agents for cGVHD control. “Steroid-refractory” cGVHD has most commonly been defined as either progressive manifestations despite one month of treatment, or incomplete response despite two months of 1-2 mg/kg of prednisone or equivalent.¹ In addition to steroid-refractoriness, other clinical indications for additional lines of systemic immune suppressive therapy include steroid dependence and steroid intolerance. Patients with steroid-dependent cGVHD can't tolerate tapering prednisone due to recurrent cGVHD manifestations. Steroid intolerant patients have medical complications of steroid therapy (e.g. hyperglycemia, edema, psychosis, osteoporosis), and thus require additional immune-suppressive agents to control GVHD and facilitate taper of prednisone. Multiple immune-suppressive therapies, including pharmacologic agents, monoclonal antibodies, and strategies such as extracorporeal photopheresis have demonstrated moderate activity in this setting, both ameliorating objective cGVHD manifestations, as well as facilitating taper of systemic steroids.²⁵ Their effectiveness is suboptimal, however, and many patients will require multiple agents to achieve disease control. A retrospective study showed that patients with cGVHD received a median of three lines of treatment and were on systemic immunosuppression for a median of 5 years. When patients stopped systemic treatment, between 30-50% of patients needed to restart treatment a median of 3-6 months later for recurrent symptoms.²⁶

In August 2017, the FDA approved ibrutinib, a Bruton's tyrosine kinase inhibitor, for the treatment of adult patients with cGVHD after failure of one or more lines of systemic immunosuppressive therapy.²⁷ There were 24 patients with skin involvement and an 88% response rate in skin was reported; however, skin involvement was not subclassified into

inflammatory manifestations (which usually respond to treatment) or sclerotic forms (which are much harder to treat).

The overall burden of cGVHD despite routine pharmacologic GVHD prophylaxis, limited response to primary and secondary therapy, and the attendant morbidity and mortality all support the need for novel approaches in cGVHD treatment, particularly the sclerotic forms.

1.4 ASSESSMENT OF THERAPEUTIC RESPONSE IN CHRONIC GVHD

Following the 2014 NIH Consensus Conference, most clinical trials use the recommended response criteria to calculate response based on change scores in nine organ-specific measures, assessed prior to study treatment and at defined points afterwards. The organ-specific change scores are used to classify responses into complete (CR, resolution of all cGVHD manifestations), partial (PR, partial resolution of cGVHD manifestations without significant worsening in any organ), stable (SD, no change in organ involvement), mixed response (MR, improvement and worsening in different organs) and progressive (PD, significant worsening in at least one organ). The overall response rate (ORR) is the CR plus PR rate.²⁸

Interpretation of previously published trials for secondary cGVHD treatment is limited by a number of factors, most notably heterogeneity in response determination. In the Phase 2 ibrutinib study that led to regulatory approval (N=42), the best ORR was 67%. Adverse events were common including fatigue, diarrhea, muscle spasms, nausea and bruising.²⁷ The publication reported that at a median follow-up of 13.9 months, 30 (70%) had stopped treatment.

1.5 GLASDEGIB (PF-04449913, DAURISMOTM)

Glasdegib (DaurismoTM) is a potent and selective oral inhibitor of the Hh (Hedgehog) signaling pathway. It is FDA-approved for use in combination with low-dose cytarabine for the treatment of newly-diagnosed acute myeloid leukemia (AML) in adult patients who are \geq 75 years old or who have comorbidities that preclude use of intensive induction chemotherapy. It is being tested for other hematologic malignancies and solid tumors.

1.5.1 Mechanism of Action

Hedgehog activation of Gli1 has been implicated in fibrotic diseases through stimulation of mesenchymal stromal cells²⁹ or fibroblasts to differentiate into myofibroblasts which produce collagen and fibrosis. There is growing evidence of the relevance of this pathway in systemic sclerosis³⁰⁻³⁴ and efforts to block this pathway therapeutically using agents such as oral

hedgehog pathway inhibitors.³⁵ Studies in murine models of cGVHD³⁶ and human clinical trials of sonidegib³⁷ and vismodegib³⁸ suggest that Hh pathway inhibitors may improve fibrosis.

Glasdegib binds to its target Smo (smoothened), a cell membrane protein in the Hh signaling pathway, interfering with activation of Gli1 and blocking effects of aberrant Hh signaling.

1.5.2 Safety Pharmacology

Glasdegib has been extensively characterized in nonclinical safety studies in rats, dogs and rabbits. Glasdegib was evaluated in safety pharmacology studies (cardiovascular, neurofunctional, respiratory), definitive toxicology assessments of up to 6- and 9-months duration, in vitro and in vivo genetic toxicity studies, local irritation study and embryo-fetal developmental toxicity studies. The primary target organs in rat included kidney, bone, and tooth. The primary target organs in the dog included kidney and liver. Additional observations of alopecia and skin irritation/inflammation, and QTc prolongation were identified in the dog.

In general, many findings in the rat and dog predict drug reactions reported in the clinic with glasdegib; these include muscle spasms, alopecia and QTc prolongation. However; not all the organ toxicities observed in animals have been observed in humans when treated with glasdegib. The kidney is a target organ in rat and dog. In the clinical program, at the 100 mg dose, acute kidney injury has been reported, primarily Grade 1-2. These events were often associated with prerenal confounders or consequent to or exacerbated by other glasdegib effects (e.g., diarrhea, vomiting, and/or decreased oral intake).

There have not been any liver events or significant increases in liver transaminases reported in the clinic. Findings in bone, teeth and testis are considered a potential concern only for pediatric patients, as Hh signaling is important in growth and development of these tissues. These effects have not been seen in adult patients and are not a risk for adults being treated with glasdegib.

Based on the available clinical data, the safety profile of glasdegib as a single agent administered orally on a once daily continuous dosing regimen is characterized by manageable and potentially reversible toxicities that are generally mild to moderate in severity. The key observed toxicities are: muscle spasms, dysgeusia, decreased appetite, and alopecia. Glasdegib can cause embryo-fetal death or severe birth defects when administered to a pregnant woman. Glasdegib is embryotoxic, fetotoxic, and teratogenic in animals.

For further details on the safety pharmacology of glasdegib, refer to the Investigator Brochure.

1.5.3 Drug-drug Interaction Potential

For more detailed information on drug-drug interaction potential for glasdegib, refer to the Investigator Brochure.

Please refer to [Section 3.8 Concomitant Therapy](#) for guidance on drugs that may cause drug-drug interactions.

1.6 CLINICAL EXPERIENCE – GLASDEGIB

For more detailed information on the clinical experience for glasdegib, please refer to the Investigator Brochure.

1.6.1 Clinical Efficacy

There have been no reports of the use of glasdegib for cGVHD. Glasdegib is FDA-approved at a dose of 100 mg daily in combination with low-dose cytarabine for the treatment of adult patients with acute myeloid leukemia for whom intensive chemotherapy is not an option. It is currently under investigation as treatment for hematologic and solid tumor malignancies. An ongoing Spanish study of glasdegib for sclerotic cGVHD identified 50 mg daily at the recommended dose ([name], personal communication). However, the Spanish study will not be sufficient to confirm the tolerability of glasdegib at this dose or provide robust efficacy data, so the present study is still warranted.

1.6.2 Adverse Events

The table below lists the most common treatment emergent/treatment-related adverse events (AE) of special interest seen thus far in 5 or more patients receiving glasdegib alone or in combination with chemotherapy (N=241). Most studies combined glasdegib with other chemotherapy making it difficult to ascertain toxicities due to glasdegib itself. Liver toxicity and neuropathy have not been identified as drug-related in the clinical program.

TABLE 2. The most common adverse events seen with glasdegib.

System Organ Class Preferred Terms	Grade 3	Grade 4	Grade 5	Total
Any AEs	63 (26.1)	72 (29.9)	3 (1.2)	194 (80.5)
Blood and lymphatic system disorders	62 (25.7)	68 (28.2)	0 (0.0)	138 (57.3)
- Anaemia	58 (24.1)	4 (1.7)	0 (0.0)	70 (29.0)
- Febrile neutropenia	59 (24.5)	6 (2.5)	0 (0.0)	65 (27.0)
- Thrombocytopenia	8 (3.3)	46 (19.1)	0 (0.0)	56 (23.2)
- Neutropenia	3 (1.2)	41 (17.0)	0 (0.0)	51 (21.2)
Nervous system disorders	0 (0.0)	0 (0.0)	0 (0.0)	87 (36.1)
- Dysgeusia	0 (0.0)	0 (0.0)	0 (0.0)	82 (34.0)
- Ageusia	0 (0.0)	0 (0.0)	0 (0.0)	8 (3.3)
Musculoskeletal and connective tissue disorders	11 (4.6)	0 (0.0)	0 (0.0)	67 (27.8)
- Muscle spasms	8 (3.3)	0 (0.0)	0 (0.0)	52 (21.6)
- Myalgia	3 (1.2)	0 (0.0)	0 (0.0)	16 (6.6)
- Musculoskeletal pain	0 (0.0)	0 (0.0)	0 (0.0)	6 (2.5)
Infections and infestations	27 (11.2)	9 (3.7)	3 (1.2)	64 (26.6)
- Pneumonia	9 (3.7)	2 (0.8)	1 (0.4)	15 (6.2)
- Device related infection	3 (1.2)	1 (0.4)	0 (0.0)	7 (2.9)
- Sepsis	1 (0.4)	5 (2.1)	1 (0.4)	7 (2.9)
Skin and subcutaneous tissue disorders	0 (0.0)	0 (0.0)	0 (0.0)	48 (19.9)
- Alopecia	0 (0.0)	0 (0.0)	0 (0.0)	48 (19.9)
Investigations	4 (1.7)	0 (0.0)	0 (0.0)	17 (7.1)
- Electrocardiogram QT prolonged	4 (1.7)	0 (0.0)	0 (0.0)	17 (7.1)
Renal and urinary disorders	3 (1.2)	0 (0.0)	0 (0.0)	7 (2.9)
- Acute kidney injury	2 (0.8)	0 (0.0)	0 (0.0)	6 (2.5)

1.6.3 Warnings and Precautions

1.6.3.1 Cytopenias

Febrile neutropenia was reported in 41% of patients being treated for myeloid malignancies, usually in combination with other chemotherapy. In patients receiving single agent glasdegib, cytopenias were reported only sporadically, with no Grade 3 / 4 events. Complete blood counts (CBC) will be monitored in this study.

1.6.3.2 QT/QTc

QTc prolongation has been observed in studies with glasdegib although usually in patients with multiple comorbidities, including significant cardiovascular medical history, and/or in patients taking concomitant therapy with QT prolonging potential. None of the events were accompanied by serious cardiac arrhythmias. Although the likelihood of QT prolongation is low, ECGs will be monitored in this study and patients with significant cardiac histories excluded.

1.6.3.3 Renal impairment

The incidence of grade 3 or higher creatinine levels was less than 5% and occurred in patients with multiple potential other contributing factors. Renal function will be monitored in this study and patients with significant baseline renal dysfunction excluded.

1.6.3.4 Muscle spasms

Muscle spasms are on-target adverse events and are considered a class effect for SMO inhibitors. No cases of rhabdomyolysis have been reported with glasdegib. In prior studies, grade 3 muscle spasms were seen in 1.2%. Patients with muscle spasms should receive adequate hydration and electrolyte imbalances should be corrected. Stretching may be helpful. Some have tried low-dose calcium channel blockers. Approximately 18% of those who had muscle cramps had ongoing symptoms at the time of treatment discontinuation, although mostly at low level.

1.6.3.5 Hyponatremia

Hyponatremia was observed in some patients, usually grade 3 or less. There was a single case of grade 4 hyponatremia that could have been related to a concurrent medication that resolved the next day. Electrolytes will be monitored in this study.

1.6.3.6 Dysgeusia

Dysgeusia is an on-target adverse event and is considered a class effect for SMO inhibitors reported in about 40% of patients, although almost always grade 1/2 and infrequently leading to treatment discontinuation. Approximately 41% of patients who had dysgeusia had ongoing symptoms at the time of treatment discontinuation.

1.6.3.7 Alopecia

Alopecia is an on-target adverse event and is considered a class effect for SMO inhibitors with 19.9% reported events, although almost always grade 1/2 and rarely leading to discontinuation. Of patients with alopecia, 75% had ongoing symptoms at the time of treatment discontinuation.

1.6.3.8 Dental effects

Loose teeth and toothache were observed in fewer than 10% patients taking glasdegib in combination with chemotherapy.

2.0 STUDY OBJECTIVES

2.1 PRIMARY OBJECTIVE:

Determine whether 50 mg daily of glasdegib is safe and tolerable in the cGVHD population.

2.2 SECONDARY OBJECTIVES:

2.2.1. Determine best overall response rate by 12 months (complete response + partial response) for sclerotic manifestations of cGVHD.

2.2.2. Determine best overall response rate by 12 months (complete response + partial response) for all manifestations of cGVHD.

2.2.3. Examine the safety profile of glasdegib in the cGVHD population.

2.2.4. Bank blood and skin biopsy material for future biologic studies.

3.0 STUDY DESIGN

[figure not shown]
This is a single-arm, open-label, phase I/II trial examining the efficacy and safety of glasdegib 50 mg daily for treatment of sclerotic cGVHD. The FDA approved dose is 100 mg of glasdegib daily in the treatment of AML. The MTD in other glasdegib studies in healthy and cancer patients is 400 mg daily.

Twenty subjects will be enrolled. A subject is considered enrolled the day the informed consent form is signed. To control the speed of enrollment and ensure that no more than 20 subjects are enrolled across the study, each participant must be approved by the coordinating center at Fred Hutchinson Cancer Research Center prior to enrollment.

Eligible subjects will undergo up to 24 cycles of study therapy. At this point, there is no study support for longer glasdegib administration or monitoring. If study drug is discontinued prematurely, subjects will still complete remaining study assessments every 3 months through 24 months, unless they refuse continued active participation, relapse, or start a new systemic immunosuppressive treatment, in which case they are followed by chart review only. If subjects discontinue study drug within the first 6 months of study participation (prior to C7D1), they should be seen next at the time point that coincides with an overall every-3-month visit cadence (i.e. C4D1 or C7D1, whichever is next). Any monthly visits in the interim are not required for patients who have stopped glasdegib.

Refer to Appendix 2 for a comprehensive list of study assessments and their timing. The study schema is provided below (FIGURE 1).

Figure 1. Study Schema

3.1 STUDY PARAMETERS

3.1.1 Efficacy Parameters

See Section 5.5.1 for definitions.

3.1.2 Safety Parameters

The safety of glasdegib will be characterized by the type, frequency, severity, timing of onset, duration, and relationship to study drug of any treatment-emergent grade 3 or higher AEs, any severe adverse events (SAE) or AEs leading to discontinuation of study treatment or death.

The severity of AEs will be graded using the Common Terminology Criteria for Adverse Events (CTCAE), version 5.0. Standard definitions for seriousness will be applied (see Section 6.1).

3.2 RATIONALE FOR STUDY DESIGN AND DOSING REGIMEN

A single arm, open-label trial is justified by the rarity of cGVHD and no prior published experience for this indication. 100 mg daily is the approved dose for acute myeloid leukemia. We will use the lower dose of 50 mg daily for 28 days to assess tolerability based on the preliminary experience of a Spanish group conducting a similar trial. Only adults will be enrolled given the lack of data in pediatric populations.

3.3 SELECTION OF STUDY POPULATION

3.3.1 Inclusion Criteria

Eligible subjects will be considered for inclusion in this study if they meet **all** of the following criteria:

1. At least 18 years old
2. Diagnosed with moderate or severe cGVHD according to the 2014 NIH Consensus Criteria
3. Diagnosed with cGVHD-related sclerosis or fasciitis
 - Skin feature score of at least 2 OR
 - Joints and fascia score of at least 1
4. New, stable or progressive sclerosis/faciitis despite treatment with at least one prior line of systemic therapy for cGVHD.
5. Female patients who:
 - Are documented to be postmenopausal or are surgically sterile, OR

- If of childbearing potential, agree to use at least 1 highly effective method of contraception from the time of signing the informed consent form through 30 days after the last dose of study drug, OR agree to practice true abstinence or exclusively non-heterosexual activity when this is in line with the preferred and usual lifestyle of the subject

6. Male patients who:

- Are surgically sterile (vasectomized) OR
- Agree to use at least 1 highly effective method of contraception during the entire study treatment period and through 30 days after the last dose of study drug, OR agree to practice true abstinence or exclusively non-heterosexual activity when this is in line with the preferred and usual lifestyle of the subject, AND
- Agree to use a condom to prevent potential transmission of investigational drug in seminal fluid

7. Patients who meet the following clinical laboratory criteria:

- Absolute neutrophil count (ANC) >1000/ μ L, platelet count >50 \times 10⁹/mL
- ALT and AST < 2x ULN and normal total bilirubin unless attributed to cGVHD
- Creatinine < 2.0 mg/dL

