- If a DSMB review is required because the stopping rule is triggered, patients who are already enrolled and taking glasdegib may continue treatment, pending the outcome of that review. Any enrolled patient who has consented but not started study drug may not start glasdegib treatment, pending the outcome of that review.
- The DSMB may, after review, recommend to stop the trial or continue it with or without modifications.

We will also include a stopping rule for grade ≥ 3 AEs that are known to be adverse reactions to glasdegib and hedgehog inhibitor pathway class drugs, such as musculoskeletal pain, muscle spasm, QT prolongation, anorexia, nausea, diarrhea, dizziness, elevated creatinine, elevated

transaminases, and tooth problems. If the lower bound of an 80% exact binomial confidence interval is > 20%, operationally given the total sample size 20, if any 2 of the first 4 or fewer subjects or any 3 of the first 7 or fewer subjects or any 4 of the first 11 or fewer subjects or any 5 of the 15 or fewer subjects or 6 of the first 20 or fewer subjects have unacceptable toxicity or Grade 3 or higher severity AEs, then enrollment will be halted while the DSMB reviews the study. If the true probability of Grade 3 or higher AE is 5%, the probability of study suspension under the above rule is approximately 0.02; if the true probability is 40%, the probability of suspension is approximately 0.85 (probabilities estimated from 5,000 simulations, using R version 3.5.0).

Since 2 of the first 4 patients experienced grade 3 muscle cramping, the stopping rule was triggered. Of note, these 2 patients had cramping prior to enrollment. The DSMB reviewed the data and allowed enrollment to continue but with an exclusion criterion for pre-enrollment grade 2 or 3 muscle cramps, or grade 1 cramps that occur at least weekly. For the purposes of the stopping rule, we will start again with subject #5, so if 2 of the next 4 or fewer, 3 of the next 7 or fewer, 4 of the next 10 or fewer, or 5 of the next 15 have unacceptable toxicity or grade 3 or higher severity AEs, then enrollment will be halted again while the DSMB reviews the study. If the true probability of Grade 3 or higher AE is 5%, the probability of study suspension under the above rule is approximately 0.02; if the true probability is 40%, the probability of suspension is approximately 0.85 (probabilities estimated from 5,000 simulations, using R version 3.5.0).

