cGVHD Overall	 Very much better (+3)	 Moderately better (+2)	 A little better (+1)	 About the same (0)	 A little worse (-1)	 Moderately worse (-2)	 Very much worse (-3)
	Write in →	What are your reasons for how you rated "chronic GVHD overall"? (For example, has a specific organ or symptom improved or worsened?)					

Other complications related to chronic GVHD:					
	Never (0)	Past, not now (1)	Mild (2)	Moderate (3)	Severe (4)
1. Ascites (serositis)					
2. Pericardial Effusion					
3. Pleural Effusion(s)					
4. Nephrotic syndrome					
5. Myasthenia Gravis					
6. Peripheral Neuropathy					
7. Polymyositis					
8. Weight loss >5% without GI symptoms					
9. Eosinophilia >500/ul					
10. Platelets <100,000/ul					
11. Other, please specify: a. _____					

Clinician Signature: _____ Date: _____

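### The platelet inclusion limit is printed per mL, a value no patient could plausibly meet; the unit or exponent needs correcting in both places (low severity)

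*Combined protocol and SAP*

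**What the plan says.** Section 3.3.1 introduces its list with "Eligible subjects will be considered for inclusion in this study if they meet" and goes on to require every listed criterion, so failing any one of them makes a patient ineligible. The first bullet of criterion 7 sets an ANC limit above 1000 per microlitre and, beside it, "platelet count >50" × 10⁹ per mL. Criterion 7 in the Study Synopsis repeats this as "platelet count > 50" × 10⁹ per mL.

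The other platelet figure expressed as a count is in the Appendix 6 provider form, where "Platelets <100,000/ul" is one item on a checklist of complications related to chronic GVHD. No section corrects or explains the per-mL unit in criterion 7.

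The criterion is operative. Section 4.1.5 has eligibility assessed against Sections 3.3.1 and 3.3.2, Section 3.3.3 has the patient enrolled once eligibility is confirmed, and Section 3.0 requires coordinating-center approval of each participant.

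**The concern.** A platelet count in the tens of billions per mL is far outside the scale on which the protocol itself reports platelets. If the printed limit cannot be met, the protocol does not contain the threshold that was used to admit patients.

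What is at stake is the written record of eligibility. Section 3.12 gives the coordinating-center investigator responsibility for procedures that assess protocol compliance, and it provides for monitoring at each site by staff independent of the study team. Anyone checking a patient's platelet count against Section 3.3.1 has to substitute a limit that is not written there. Safety and tolerability are the primary objective, so an entry limit on a blood count should be readable as it stands.

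**Working it through.** This is a unit conversion. The plan derives no figure here that could be reproduced.

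**Inputs**
- Printed limit: 50 × 10⁹ per mL (Study Synopsis and Section 3.3.1, criterion 7).
- Scale used elsewhere: ANC per microlitre (same bullet); platelets per microlitre (Appendix 6).
- Conversions: 1 mL = 1,000 µL; 1 L = 1,000 mL = 1,000,000 µL.
- Assumption, not from the documents: human platelet counts do not exceed about 5,000,000/µL.

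**Step 1. Convert the printed limit.**
50 × 10⁹ per mL ÷ 1,000 = 50,000,000 per µL.

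**Step 2. Compare it with assumed counts** (limit ÷ count):
- 50,000/µL: 50,000,000 ÷ 50,000 = 1,000
- 150,000/µL: 333
- 450,000/µL: 111
- 1,000,000/µL: 50
- 2,000,000/µL: 25
- 5,000,000/µL: 10

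No count in this range meets the criterion, and the shortfall is still tenfold at the top of it.

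**Step 3. Check the scale inside the protocol.**
The Appendix 6 item is 100,000/µL, and 50,000,000 ÷ 100,000 = 500. That item flags a complication. It is neither an eligibility limit nor a normal range, so the ratio shows only that the two platelet figures sit on different scales. It does not measure how wrong the limit is.

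**Step 4. See what a single-character slip would imply.**
- mL printed for L: 50 × 10⁹ per L ÷ 1,000,000 = 50,000/µL. The printed value is then 50,000,000 ÷ 50,000 = 1,000 times too high.
- Exponent 9 printed for 6: 50 × 10⁶ per mL ÷ 1,000 = 50,000/µL, again a factor of 1,000.

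Both slips lead to the same number. This shows how little ambiguity a reader would face. It does not establish what the sponsor intended.

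**Step 5. Compare with conduct.**
Section 3.12 reports: "Since 2 of the first 4 patients experienced grade 3 muscle cramping". Under Section 6.2.1, apart from events due to screening procedures, adverse events are collected from the first dose onward. Patients had therefore been admitted and treated. Given the assumption above, they cannot have been admitted under the printed limit.

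**The case against.** The best reply is that this is a typographical slip with no practical effect. Experienced hematology sites would recognise it, and the two obvious corrections give the same limit. Every participant also needs coordinating-center approval under Section 3.0, so there is one common check. Most of this stands, and it is why the severity is low. Central approval does not, however, put the missing threshold into the protocol.

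A text-conversion fault could also be suspected, since exponents and units are fragile in that step. Appearing twice does not rule it out, because both places come from the same file. The same unit in two differently formatted places makes it unlikely, and a look at the source file would settle it.

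A reader might go further than the documents allow in three ways:
- **That every enrolled patient is an eligibility deviation.** This follows only from a literal reading that nobody appears to have used. The documents record no such deviation, and Section 3.12 describes the DSMB reviewing the data and letting enrollment continue.
- **That the three centers used different limits.** There is no evidence of inconsistent application.
- **That the trial's statistical properties are affected.** The platelet limit does not enter the sample size, the Simon two-stage design, the stopping rules or any endpoint definition.

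**Conclusion.** Wrong as written, low severity. As printed, the limit equals 50,000,000/µL, and on the stated assumption of counts up to about 5,000,000/µL no patient could meet it. Because patients entered the trial, the limit in use was not the one in the text. The likely cause is a unit or exponent error, 1,000-fold if per litre was meant. That factor is conditional on the sponsor's intent, which the documents do not state. The fault lies in the documentation of one mandatory criterion; the documents do not show that it changed who was enrolled.

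**What to change.** Correct the unit or exponent of the platelet limit in criterion 7, in the Study Synopsis and in Section 3.3.1 together, so that both agree with the per-microlitre scale used for ANC and in Appendix 6. The sponsor should confirm the intended limit; none is proposed here. It would help to state in the amendment or a note to file which limit was applied to patients already enrolled, so that their eligibility can be checked against a written value. The cost is a unit correction in two places, with no new data and no change to the analysis.
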